Medication. Hypertensive patients will be treated with distinctively colored, *odored and flavored* gelatine capsules (Capsuline, Inc, Pompano Beach, FL) containing 12.5 mg (generic version, available from the Strong Memorial Hospital Research Pharmacy). The “placebo” will be a capsule containing 12.5 mg of an inert substance with the same characteristics as the active drug capsules. Capsules will be packaged in a blister strip of single application packets by the Investigational Drug Studies program in the Strong Memorial Hospital Research Pharmacy. Preparation of the sequence of medication would be done from coded patient numbers and would depend upon the schedule of reinforcement that was being used. For example, if one were imposing a 25% reinforcement schedule (only one fourth of the packets of capsules containing active drug), a random sequence would be constituted with the proviso that the patient would receive no more than two doses of consecutive placebo capsules. Randomization will be performed by the research pharmacy in blocks of eight. Allocation concealment will be guaranteed, since only the research pharmacist will be aware of group distribution and all other members of the research team will be blinded. He will provide the research nurse with the pre-labeled packages.

Length of study: 8 weeks for those subjects that complete the full set of procedures. For those subjects who relapse early, or whose blood pressure does not remit (10-point decrease for a period of 5 days) prior to the Exp 1 phase, the minimal period in the study is 3 weeks.

Exp 1: Baseline Period: 2 weeks after a screening physical examination that will be performed within one week of admission. ; Experimental Phase: 2 weeks (or less for subjects' whose mild hypertension relapses). Therefore, maximal possible period receiving carvedilol: 4 weeks.

Exp 2: 4 weeks. In this experiment subjects either receive placebo or no treatment. We expect the latter group to relapse after a few days. Those receiving placebo are hypothesized to relapse later, and we are assuming that will relapse before 4 weeks on placebo. However, if we find that there are subjects that after 4 weeks have not relapsed, we plan to continue the administration of the placebo until they relapse (beyond the 4 weeks). Because we believe that this will occur rarely, for practical reasons we will state in the consent form that this period may last “up to 4 weeks”.

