It is possible that the therapeutic effects of a partial schedule of pharmacologic reinforcement (and, thus, a reduced amount of active drug) will be indistinguishable from a continuous (standard) regimen of pharmacotherapy. That outcome, however, is not critical for evaluating the role of conditioning in pharmacotherapies simply because these groups would have received different amounts of drug. Specifically, *it is hypothesized that patients treated under a noncontinuous schedule of medication will be less likely to show a recurrence of symptoms ("relapse") than patients treated with that same amount of drug administered under a continuous schedule of reinforcement.*

On the first visit, each potential subject will undergo a brief physical examination to record the medical history, sign an informed consent form, and receive instruction in the use of a blood pressure monitor. A strip of medication packets will be supplied at each clinic visit and will be taken by the subject at home, 2

times a day for the duration of the study.. The subject will return to the study center once a week or within 14 days of the drug dispensing cycle; this will allow flexibility for those with travel or work schedule challenges. The study coordinator will email or call to check on safety of the subject in the interim of a weekly clinic visit. Each drug card contains 15 days of study drug to ensure continual dosing in the event a weekly visit is missed. Packets containing medication will be dispensed by code so the patient and the physician will be blinded as to the nature of the medication. To consider the possibility that conditioning might be influenced by immediate stressful life experiences in these patients, we will examine this relationship using two measures of psychological distress administered at weekly intervals: the Hassles Scale, a frequently-used measure of daily stressors or “hassles” and the Impact of Events Scale (IES) (31).

The protocol for Experiment 1 is shown in Table 1. During a baseline period (of a maximum of 15 days), all patients will be treated BID with 12.5 mg. Those who satisfy the criterion of a 10-point decrease in blood pressure for a period of 5 days will be assigned randomly to experimental groups.

During the 15-day experimental period, the patients will be treated as follows:

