The primary outcome measure will be the incidence and rate of “relapse,” defined as a blood pressure level that has risen to the baseline value (blood pressure value of the participant at the time of enrollment) for three consecutive days.

If, over the course of 15 days there is evidence of a gradual recurrence of symptoms, the experimental period can be extended. If there is no evidence of impending relapses, there are two options: (a) we can reduce the partial reinforcement schedule from 25% to 15%, for example, and adjust the dose of in the Dose Control Groups accordingly; or (b) proceed to a study of extinction effects (Experiment 2).

Timeline estimate. We propose a start-up period of 6 mo. (formulation of Consent Form, IRB approval of protocol, preparation of study personnel, data management procedures, preparation and placing of advertisements for study subjects, etc). Including an instructional session and testing of blood pressure measurements from the monitors provided to patients, patients enrolled in the study could be engaged for as many as 50-60 days. We calculate being able to process 40 patients/year. A final 6 mo. would be devoted to data processing and manuscript preparation and, thus, a total project period of 4 years.

Experiment 2. *Effects of CS exposure on the persistence of drug effects following the withdrawal of drug and the effects of partial schedules of pharmacotherapeutic reinforcement on resistance to extinction.*

Based on the time available and the outcome of Experiment 1, we may be able to gather additional preliminary data on the extinction of conditioned pharmacotherapeutic effects, adding evidence that results obtained in Experiment 1 are, in fact, the results of conditioning. We expect that patients in Dose Control Group-II from Experiment 1 will relapse within 2-3 days of the treatment imposed during the experimental period. A large percentage of Dose Control Group-I patients are also expected to relapse under a reduced dose of active drug during the experimental period. However, we expect that a significant percentage of patients in the Partial Reinforcement Group (as well as the Standard Therapy Group) would be available for further study of extinction effects.

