If, as anticipated, there are a sufficient number of patients from Experiment 1 who show no evidence of relapse within the 15-day experimental period, we can proceed to Experiment 2. The remaining patients from the Standard Therapy and Partial Reinforcement Groups (and, perhaps, the Dose Control Group-1) would be divided into two subgroups. For one subgroup, all medication would be discontinued for a period of 2-4 wk; for the other subgroup, active drug would be discontinued but the patients would continue to receive the distinctive capsules containing inert substance. It is predicted that: (a) patients reexposed to the CS will be less likely to relapse or show a slower rate of relapse than patients in groups that are not reexposed to the CS; and (b) patients in the Partial Reinforcement Group will be more resistant to extinction (slower to relapse) than patients remaining from Dose Control Group-1 who were treated with the same cumulative amount of drug and may even be indistinguishable from the Standard Therapy Group that had received three times more drug. An alternative strategy, of course, would be to enlist a new population.

c) Statistical Analysis: Data analyses are described separately for each of the specific hypotheses. All statistical tests will be two-sided with $p \leq .05$. The principal analyses focus on the difference over 2-weeks between PR and two dose control groups (DC-1 and DC-2) in Experiment 1. The main independent variable is time to relapse as well as symptom reduction (blood pressure). These two outcomes will also be examined in Experiment 2 to see if they differ between the two groups (placebo and no-treatment groups). Because power for the comparisons in the second experiment may be undercut by high relapse rates in the first experiment, this second set of analyses is exploratory.

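### Experiment 2 allows placebo past 4 weeks with no time limit, while the consent form is to state 4 weeks as the maximum

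*Combined protocol and SAP*

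**What the plan says.** Section III.a (Length of study) gives the overall duration: "Length of study: 8 weeks for those subjects that complete the full set of procedures". It sets Experiment 2 at 4 weeks and assumes that placebo patients will relapse within that time. For those who do not, the rule is: "we plan to continue the administration of the placebo until they relapse (beyond the 4 weeks". The protocol then explains the consent wording: "Because we believe that this will occur rarely, for practical reasons we will state in the consent form that this period may last", and the limit to be stated there is 4 weeks.

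The event that ends the extension is relapse, which the Experiment 1 text gives as the primary outcome: "defined as a blood pressure level that has risen to the baseline value (blood pressure value of the participant at the time of enrollment", sustained for three consecutive days. No separate definition is given for Experiment 2.

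The Experiment 2 section attaches a duration to the untreated subgroup: "For one subgroup, all medication would be discontinued for a period of 2-4 wk". The other subgroup continues on inert capsules, with no separate duration. The timeline estimate says that "patients enrolled in the study could be engaged for as many as 50-60 days", and the last payment in section V covers weeks 5 to 8. Section III.c says of the Experiment 2 comparisons that "this second set of analyses is exploratory".

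**The concern.** The protocol plans an exposure that can be longer than the one it intends to disclose, and it does so knowingly. A patient who has not relapsed at day 28 would stay on placebo, off carvedilol, for longer than the consent form says, until an event that may never occur.

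What is at stake is the accuracy of consent and the lack of a planned end to one treatment period. The stated duration matters more than usual here. Section V (Debriefing Procedures) withholds the word placebo until debriefing, and section III.a keeps the medical staff whom the patient meets unaware of whether or when medication is reduced. The duration is therefore one of the few facts that tell a patient how long reduced or absent treatment might last. No primary inference is at stake.

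**Working it through.** This is mainly a comparison of texts, with little arithmetic.

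**1. The plan's own figure.** From section III.a: baseline 2 weeks + experimental phase 2 weeks + Experiment 2 4 weeks = 8 weeks = 56 days. This reproduces the stated study length, lies within the 50 to 60 day estimate, and matches the payment schedule, which ends at week 8. All three describe a nominal schedule in which Experiment 2 stops at 4 weeks.

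**2. The two maxima side by side.**

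| Source | Longest placebo period in Experiment 2 |
|---|---|
| Planned consent wording (III.a) | 4 × 7 = 28 days |
| Planned conduct (III.a) | until relapse; no maximum |

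**3. Search for a limit elsewhere.**
- Experiment 2 section: the 2 to 4 weeks is attached to the untreated subgroup. It could be read as covering both subgroups, but III.a states explicitly that placebo may go on beyond 4 weeks.
- Criteria for investigator-initiated removal: these allow removal for toxicity or progressive disease, but set no time limit.
- Weekly visits, home readings, patient safety monitors and a six-monthly safety board (schedule of events, III.a, IV.c): oversight, but no time limit.
- Right to withdraw (V, Subject Capacity): available at any time, but it depends on what the patient has been told.
- Renewed consent at week 4: not mentioned.

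**4. Does the relapse rule act as a cap?** It is a numeric stop, specific to each patient, but not a time limit. Illustration, assuming that systolic pressure is used: section II.a enrols at 140 to 170, and entry to the experimental phase requires a 10-point fall for 5 days. A patient enrolled at 168 who responds and later settles at 160 is still below 168. He has not relapsed, and placebo continues.

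**5. How many patients?** The documents give no relapse rate on placebo, so the belief that extension is rare cannot be checked. As an assumption only, take exponential time to relapse with median m weeks. The share not relapsed at 4 weeks is 0.5^(4/m):
- m = 1: 0.5^4 = 6%
- m = 2: 0.5^2 = 25%
- m = 3: 0.5^1.33 = 40%
- m = 4: 0.5^1 = 50%

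The range shows only that rarity requires fast relapse on placebo. The trial's hypothesis is that placebo slows relapse, and Experiment 2 takes patients who have already come through Experiment 1 without relapsing.

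**The case against.** The best case for the plan is that the extension is stated openly in the protocol, is expected to be rare, belongs to an experiment that runs only if conditions permit, and has a statistical reason: following patients to relapse avoids censoring. A patient in the extension has by definition not had sustained pressure back at the enrolment level. All of this stands. It limits the weight of the point but does not align the consent wording with the planned conduct.

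Four stronger readings are tempting, and the documents do not support them.

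- **That the extension contradicts the 8-week study length, or breaks every stated length within days.** The 8 weeks is a nominal length to which III.a states an exception. The 50 to 60 days is an estimate, not a limit. The 15-day baseline is a maximum: if patients were randomised as soon as they had 5 qualifying days, which the text leaves unclear, the total would be 5 + 15 + 28 = 48 days. The experimental period may also be extended.
- **That patients are not told they may be off drug.** Section III.a says that they are told medication may be reduced, and section V that at times they may receive none. Only a possible duration beyond 4 weeks goes undisclosed.
- **That patients are left untreated or at high risk.** Section II.a permits several other antihypertensive classes, although the text in III on use before entry is not consistent. Section IV.b compares the delay in treatment with several months of non-drug attempts, so an extension of a few weeks need not exceed that benchmark.
- **That nothing numeric ends the placebo period.** Relapse does. What is missing is a time limit.

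**Conclusion.** The point holds in a narrow form. The plan allows Experiment 2 placebo to continue without a maximum time and intends to tell patients that 4 weeks is the maximum. Relapse is the only endpoint that the protocol specifies for the extension, so a patient whose pressure stays below the enrolment value has no planned end date.

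The size is 28 days stated against no limit planned. The number of patients affected is unknown. High risk is not shown, Experiment 1 and its primary outcome are unaffected, and Experiment 2 is conditional and exploratory. The mismatch should still be corrected before any patient enters Experiment 2, because rarity does not help the patient to whom it happens.

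The conclusion rests on two assumptions: that the relapse definition from Experiment 1 carries over to Experiment 2, and that the consent form says what the protocol plans. The form itself is not in the documents and could not be checked.

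**What to change.** Set a fixed maximum for the Experiment 2 placebo period: either 4 weeks, or a longer cap if the late data are wanted. State the same maximum in the protocol and the consent form and, if it exceeds 4 weeks, in the study length and payment schedule as well. At the cap, return patients who have not relapsed to usual care and censor them there in the Cox analysis already planned.

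The administrative cost is one stopping date and matching wording. The scientific cost is the loss of relapses after the cap. For placebo against no treatment (hypothesis 2), a 4-week cap loses little: if untreated patients are followed for at most 4 weeks, later risk sets contain only placebo patients and carry no information on that contrast. The loss falls mainly on hypothesis 3, which compares partial with continuous reinforcement among patients who are all on placebo. A longer, disclosed cap loses fewer of those events but keeps patients off carvedilol longer.

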- Subject population Characteristics: This investigation will apply the principles of conditioning described above in patients with mild (Stage 1) *hypertension*. These are patients who are normally started on a single drug and, most often, on the lowest dose recommended. In this case, we will be using, a drug currently used for the treatment of hypertension. Subjects will be 18-80 year old male and female patients **with mild hypertension** (systolic pressure between 140-170 and a **heart rate of 68 beats/minute or greater** . . .
- Number of available subjects: In the year 2004, the incidence of hypertension in the U.S. was 29% of the adult population, and rapidly rising. Patients will be recruited from the Medicine clinics of University of Rochester and affiliated Primary Care facilities. The pool of potential subjects is over 2,000.
- Acceptable disease status/condition (concomitant illnesses): Subjects should be in generally good health, and on few medications
- Must not suffer from severe or inhaler-dependent reactive airway disease (asthma or COPD).
- **Permitted or prohibited concurrent treatment:** the only classes of anti-hypertensive medications that can be used are ACE-inhibitors, angiotensin receptor blockers, calcium channel blockers, aldosterone antagonists, and diuretics. No other classes of anti-hypertensive medications are permitted.
- Time constraints for performance of pre-study (**eligibility**) tests: **If potential participant has not had blood work done within the** past year, a basic blood profile (one tube of blood) will be required to **ensure renal functions are safe for the use of carvedilol**. The blood draw can be done by research staff at the time of initial evaluation and available within 24 hours for review. Ability of the subject to provide informed consent: Only subjects able to provide informed consent will be recruited

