b) Number of Subjects: 121. Sample size and Power Analysis: The proposed study will recruit 37 subjects for each of the ST, PR and DC1 treatment conditions, and 10 subjects for the CD2 group. The study has 93% power to detect a 50% difference in relapse rate between group 2 and group 3 over the 2-week assessment period, even account for 10% dropout rate based on a two-sided $\alpha = 0.05$ using the method of Lakatos, E. (35). We selected a 50% relapse rate difference for the power calculation based on our prior experience. For the primary continuous symptom measure blood pressure, we have 80% power to detect about a medium effect size 0.56 based on a longitudinal study design with 7 assessment points, a conservative estimate of within-subject correlation 0.5, and a two-sided type I $\alpha=0.05$ using the method of Tu et al. (36). Note that although blood pressure is assessed twice daily in Experiment 1, we conservatively set the number of assessments at 7 to improve the robustness of the power estimates. Thus, the proposed sample size not only has sufficient power to detect a clinically meaningful difference in relapse rates, but also to find meaningful change patterns for blood pressure over the treatment course.

c) Sex of subjects: The male to female ratio will follow the distribution of hypertension in the Rochester area community. Pregnant or nursing females will be excluded due to the nature of the intervention (carvedilol is Category C). Females of child bearing potential will be required to use 2 birth control methods during the study in order to participate.

d) Age of Subjects: 18 to 80 years of age. Carvedilol is not intended for use in children.

e) Racial and Ethnic Origin: No restrictions. It will follow the distribution of patients seen in the Rochester area.

f) Vulnerable Subjects: None will be enrolled.

III. METHODS AND PROCEDURES

a) **Study Design.** Randomized, single blind.

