The choice of the β/α blocker for this study was based on:

a) targets receptors of the peripheral nervous system (PNS); it is a non-selective β -adrenergic blocking agent with alpha-1 blocking activity. It is approved for use in hypertension as well as heart failure. Other hypotensive drugs could have been chosen, however, their primary target is not “directly” aimed at the PNS or CNS. We are aware that ACE inhibitors decrease catecholamines, and angiotensin receptor blockers decrease vasopressin, however, for this initial study we chose a drug that is mostly associated to the sympathetic system. We believe that this will provide the best chances of success. Future studies will include alternative drugs.

b) Carvedilol has no adverse effect on glycemic control, and is the preferred β blocking agent for patients that have diabetes (as some of ours may).

c) We have preliminary published data (28) that strongly suggests the effectiveness of our conditioning paradigm in the pharmacotherapy of hypertension using a similar β blocker.

d) can be administered two times a day, leading to an enhanced number of “learned” exposures to the stimulus, and this regimen guarantees that subjects in groups that receive only one active drug

administration out of 4 will take adequate daily amounts of that will prevent them from the undesired rebound side effects of this medication that could occur if they were to have 3 days with no active drug.

Subjects will be started on the lowest recommended starting dose of 25 mg daily in 2 fractionated doses, which is reasonable given their level of hypertension (33,34). Once a reasonable blood pressure drop is achieved, they will be randomized to four experimental groups, as described in the methods section.

Potential participants will be informed that the purpose of the study is to determine if their blood pressure could be brought under control using lower amounts of medication and that, in the course of the study, the amount of medication they receive may be reduced. The medical staff with whom the patient comes in contact will not know if or when this occurs. Measurement of blood pressure during the study will be performed by the patients themselves, who will be instructed in the use of automated BP monitors (HEM-711AC, Omron Healthcare Inc., Bannockburn, IL) which will be provided. Subjects will obtain measurements twice (one after the other) in the AM and twice (one after the other) in the PM always at the same time of day.

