A screening physical examination will be performed within one week of admission into the study and only patients, who are in good health, display no contraindications for the use of beta blockers and disclaim the use of antihypertensive medication for at least 2 wk. before the start of the study will proceed to the initial maintenance or baseline period.

Patients will be excluded from participation if they use illicit drugs, were using anti-hypertensive medications within the previous 2 weeks other than ACE-inhibitors, angiotensin receptor blockers, calcium channel blockers, aldosterone antagonists, or diuretics **Patients will be excluded from participation if they use illicit drugs; they use inhalers regularly to control reactive airway diseases like COPD and asthma;** if pregnant or if sexually active women are not using contraceptives; if they cannot be followed or monitored appropriately; or renal insufficiency are determined, which may require a blood draw at the time of screening physical examination if subject has not had basic blood profile done in the past 12 months.

Experiment 1. Effects of a partial schedule of pharmacotherapeutic reinforcement in maintaining the therapeutic effects of in the treatment of hypertension.

The proposed research will determine if, capitalizing on conditioned pharmacotherapeutic effects, patients suffering from hypertension can be effectively treated with smaller cumulative amounts of a beta blocker, . Some patients in this initial experiment will be treated on a partial rather than a continuous schedule of pharmacologic reinforcement. These patients will be compared to: (a) patients that continue to be treated on a standard regimen of pharmacotherapy at the baseline dose, and (b) patients that receive the same (reduced) total amount of medication under a continuous schedule of reinforcement as that received by experimental patients being treated under a partial schedule of reinforcement, and another Dose Control Group that receives at the same dose and frequency as the Partial Reinforcement Group, but receives no interspersed exposures to the CS.

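### The entry rules conflict on background antihypertensives, and no rule keeps the permitted ones stable although blood pressure decides both randomisation and relapse (minor)

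*Combined protocol and SAP*

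**What the plan says.** **Entry.** Three provisions bear on background antihypertensives.

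- Section III.a, screening paragraph: only patients who "disclaim the use of antihypertensive medication for at least 2 wk. before the start of the study" go on to the baseline period. No class is exempted.
- Section III.a, next paragraph: patients are excluded if they "were using anti-hypertensive medications within the previous 2 weeks other than ACE-inhibitors, angiotensin receptor blockers", calcium channel blockers, aldosterone antagonists or diuretics. The window is the same 2 weeks, but five classes are exempt.
- Section II.a, concurrent treatment: "the only classes of anti-hypertensive medications that can be used are ACE-inhibitors" and the same four further classes.

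**Use of blood pressure.** In Experiment 1, "Those who satisfy the criterion of a 10-point decrease in blood pressure for a period of 5 days" are randomised. Relapse, the primary outcome, is a return to the "blood pressure value of the participant at the time of enrollment" for three consecutive days.

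**Monitoring.** "Measurement of blood pressure during the study will be performed by the patients themselves", morning and evening. Patients attend "once a week or within 14 days of the drug dispensing cycle", and the coordinator emails or calls between visits to check on safety. The Schedule of Events lists concomitant medications at baseline and weekly. The removal criteria do not mention a change in background therapy.

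**Analysis.** Section III.c (Aim 1a) puts into the Cox model only those covariates that differ significantly between groups at baseline. Background therapy is not named there, and no stratification by it is stated.

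**The concern.** A patient taking an ACE-inhibitor fails the first entry rule and passes the other two, so screeners could reasonably decide differently. It is also unclear whether the trial studies carvedilol as first treatment or as an add-on.

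The larger gap appears once the class list is taken to govern. A background drug at a constant dose is already reflected in the patient's own enrolment value, and hence in both thresholds. A drug started or increased later is not. In the run-in it can supply the qualifying fall without a response to carvedilol, although the conditioning hypothesis depends on that response. If continued, it also keeps pressure below the enrolment value afterwards. After randomisation it can prevent a relapse. Patients see their own readings and are told that their medication may be reduced, so a rise could prompt such a change. Relapses are expected mostly in Dose Control-1 (DC-1), so prevented relapses would tend to shrink its contrast with Partial Reinforcement (PR).

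**Working it through.** **1. Which entry rule governs?** The five-class list appears twice, once as the concurrent-treatment rule and once as the exclusion over the same 2 weeks. The unqualified sentence appears once. Two statements fit an untreated population: section II.a describes patients normally started on a single drug, and section IV.b says treatment may be delayed. The list is therefore the probable rule, not a certain one.

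**2. Is there a stability rule?** I looked in the eligibility criteria, Experiment 1, the Schedule of Events, the removal criteria and section IV.b. None requires a stable dose before entry, forbids a start or increase, or says how one is handled. Recording is not restriction. The word delayed in section IV.b belongs to a risk statement.

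**3. The plan's power figure.** Section II.b states: "The study has 93% power to detect a 50% difference in relapse rate between group 2 and group 3", with 37 per arm, 10% dropout and two-sided 0.05. Arm-specific rates are not given, so 93% cannot be reproduced uniquely. With 33 per arm (37 × 0.9 = 33.3), the two-proportion formula

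power = Φ[(d − 1.96·SE0)/SE1], SE0 = √(2·p̄(1−p̄)/n), SE1 = √([p1(1−p1) + p2(1−p2)]/n)

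gives 93.1% for 80% vs 40%, 99.2% for 75% vs 25%, and 69.6% for 60% vs 30%. The last pair is also a 50% relative reduction, but it does not represent a 93% design.

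**4. Illustration of masking.** Assume that a random share f of each arm cannot relapse, whatever their blood pressure. Each relapse rate is then multiplied by (1 − f). At f = 20%, 70% vs 30% becomes 56% vs 24%: 14 points of relapse are prevented in DC-1 and 6 in PR, and the difference falls from 40 to 32 points. By the formula with n = 37 and no dropout:

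- p̄ = 0.40, SE0 = √(0.48/37) = 0.1139, SE1 = √(0.4288/37) = 0.1077
- (0.32 − 1.96 × 0.1139)/0.1077 = 0.90, so power is about 82%, against 94.7% at f = 0

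Time-to-event simulation (37 per arm, 15 days, 10% dropout, exponential relapse, at least 4,000 trials per cell; Cox model for the first two rows, log-rank for the third) gave:

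| DC-1 vs PR relapse (assumed) | f = 0 | 5% | 10% | 20% |
|---|---|---|---|---|
| 70% vs 30% | 93.9% | 92.2% | 88.7% | 80.3% |
| 60% vs 20% | 94.2% | 92.6% | 90.0% | 83.0% |
| 80% vs 40% | 96.0% | 93.0% | 90.3% | 82.9% |

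Log-rank repeats of the first two rows agree within about 3 points. The first two pairs were chosen because their power lies near 93%.

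**5. A different assumption gives the opposite result.** Lowering each arm's relapse rate by 20 points is not the same model. It turns 70% vs 30% into 50% vs 10%. Then p̄ = 0.30, SE0 = √(0.42/37) = 0.1065, SE1 = √(0.34/37) = 0.0959, and (0.40 − 0.2088)/0.0959 = 1.99, so power is about 98%.

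**6. The covariate.** Under randomisation, a significance screen at 0.05 across groups of 37, 37, 37 and 10 selects background use in 4.6% to 5.0% of trials (prevalence 10% to 50%), however prognostic it is. With an assumed prevalence of 30% to 50% and hazard ratio of 0.33 to 0.5, prespecified adjustment adds 0.7 to 2.5 points where power is about 94%. At 10% prevalence it adds 0.1 to 1.0. If background use is not prognostic, the loss is at most about 0.5 points.

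**The case against.** The best reply is that little is likely to happen. The entry conflict looks like one leftover sentence. To mask a relapse, a patient must notice a rise, have a drug started or increased, and respond to it, all before three consecutive days at the enrolment value. A later change does not undo the event. Contact between visits and weekly medication recording may bring a change to light, and section IV.b suggests that new treatment is not expected. The share of patients affected is an assumption, and random immunity is cruder than a change triggered by blood pressure. All of this stands, and it is why the point is minor. It does not remove the gap: detection does not prevent a change, the contact between visits is described as a safety check, and removal for not following study directions has no force when no direction on background drugs exists.

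A reader might infer more than the documents support:

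- **Bias between PR and DC-1 from background use at entry or a run-in change.** Both precede randomisation and are balanced in expectation.
- **A much larger loss of power, from the 60% vs 30% scenario.** That scenario starts well below the stated 93%.
- **A larger loss because changes would concentrate in DC-1.** This is plausible in direction, but nothing in the documents gives it a size.

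**Conclusion.** The point holds in a limited form. The entry wording conflicts, the five-class list probably governs, and no rule keeps permitted background therapy stable while blood pressure decides randomisation and the primary outcome. The likely consequences are inconsistent screening, some patients randomised without a shown response to carvedilol, and possible dilution of PR vs DC-1. The frequency of background changes is unknown. The fall from about 94% to about 92%, 89–91% and 80–85% rests entirely on the assumption that 5%, 10% or 20% of each arm is made unable to relapse at random. It should not be read as a forecast. The gain from naming the covariate is about 0 to 2.5 points at the design power. Severity: minor.

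**What to change.** 1. Limit the 2-week sentence in section III.a to antihypertensives outside the five classes.
2. Require a stable dose of any permitted drug for at least 2 weeks before enrolment, with no elective change through the run-in and experimental period. Allow changes needed for safety and record their date. Do not count a 10-point fall that follows a start or increase.
3. Prespecify baseline background antihypertensive use (yes/no) in the Cox and mixed models, in place of selection by baseline significance.
4. Keep patients with a later change in the main analysis. Optionally add a sensitivity analysis that counts a start or increase as relapse on its date. Censoring alone would probably be informative.

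The cost is protocol wording, one covariate, one date field and slightly narrower eligibility. The five classes stay permitted, and concomitant medications are already scheduled for collection.
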